## **8. STUDY ASSESSMENTS AND PROCEDURES**

Please refer to the 208887 MP for the overall Study Assessments and Procedures for the study.

Information and details specific to Sub-study 1 are in Section 8.3.7, Section 8.3.10 and Section 8.4 below.

- 8.1. Efficacy Assessments**
- 8.2. Safety Assessments**

Planned time points for all safety assessments are provided in the SoA tables (Section 1.3).

### **8.3. Adverse Events and Serious Adverse Events**

- 8.3.1. Time Period and Frequency for Collecting AE and SAE Information**
- 8.3.2. Method of Recording AE and SAE Information**
- 8.3.3. Method of Detecting AEs and SAEs**
- 8.3.4. Follow-up of AEs and SAEs**
- 8.3.5. Reporting of Potentially Life-Threatening AEs to the GSK Medical Director**
- 8.3.6. Regulatory Reporting Requirements for SAEs**
- 8.3.7. Management of Pregnancy**

Details of all pregnancies in female participants will be collected after the start of study treatment and for 8 months following last dose of belantamab mafodotin.

Details of all pregnancies for female partners of male participants will be collected after the start of study treatment and 5 months following last dose of belantamab mafodotin.

**8.3.8. Cardiovascular and Death Events****8.3.9. Disease-Related Events and/or Disease-Related Outcomes Not Qualifying as SAEs****8.3.10. Adverse Events of Special Interest**

Information on belantamab mafodotin AESI are contained in the 208887 MP Section 8.3.10.

**Adverse Events of Special Interest for GSK'998**

The list of terms and reporting requirements for GSK AESI are provided below. These are selected non-serious AEs and SAEs that **must be reported to GSK** regardless of relationship to study treatment. For participants who experience signs or symptoms that may be consistent with an AESI, sites are strongly encouraged to immediately notify the GSK Medical Director of the event via email and/or phone. Documentation of potential AESIs should occur after discussion between the investigator and the sponsor/Medical Director. Even events without clear confirmation of their immunologic etiology may qualify as AESIs. Many of these events may also qualify as SAEs. Details are available in the SRM. Any event that meets the criteria described below must be reported regardless of investigator-determined relationship to study treatment or if considered immune-related (unless otherwise specified). Investigators/study coordinators/designated site personnel are required to record these experiences in the eCRF (as described in the eCRF completion guidance document) and to provide supplemental information (such as medical history, concomitant medications, investigations, etc.) about the event. Please note this table lists known AESI, additional events may be identified during the course of the study.

**Table 11 Immune-related AEs for GSK'998 Treatment**

Pneumonitis (reported as AESI if Grade $\geq 2$ )		
Acute interstitial pneumonitis	Interstitial lung disease	Pneumonitis
Colitis (reported as AESI if Grade $\geq 2$ or any grade resulting in dose modification or use of systemic steroids to treat the AE)		
Intestinal Obstruction	Colitis	Colitis microscopic
Enterocolitis	Enterocolitis hemorrhagic	Gastrointestinal perforation
Necrotizing colitis	Diarrhea	
Endocrine (reported as AESI if Grade $\geq 3$ or Grade $\geq 2$ and resulting in dose modification or use of systemic steroids to treat the AE)		
Adrenal Insufficiency	Hyperthyroidism	Hypophysitis
Hypopituitarism	Hypothyroidism	Thyroid disorder
Thyroiditis	Hyperglycemia, if Grade $\geq 3$ and associated with ketosis or metabolic acidosis (DKA)	

Endocrine (reported as AESI)		
Type 1 diabetes mellitus (if new onset)		
Hematologic (reported as AESI if Grade $\geq 3$ or any grade resulting in dose modification or use of systemic steroids to treat the AE)		
Autoimmune hemolytic anemia	Aplastic anemia	Thrombotic Thrombocytopenic Purpura (TTP)
Idiopathic (or immune) Thrombocytopenia Purpura (ITP)	Disseminated Intravascular Coagulation (DIC)	Hemolytic Uremic Syndrome (HUS)
Any Grade 4 anemia regardless of underlying mechanism		
Hepatic (reported as AESI if Grade $\geq 2$ , or any grade resulting in dose modification or use of systemic steroids to treat the AE)		
Hepatitis	Autoimmune hepatitis	Transaminase elevations (ALT and/or AST)
Infusion Reactions (reported as AESI for any grade)		
Allergic reaction	Anaphylaxis	Cytokine release syndrome
Serum sickness	Infusion reactions	Infusion-like reactions
Neurologic (reported as AESI for any grade)		
Autoimmune neuropathy	Guillain-Barré syndrome	Demyelinating polyneuropathy
Myasthenic syndrome		
Ocular (report as AESI if Grade $\geq 2$ or any grade resulting in dose modification or use of systemic steroids to treat the AE)		
Uveitis	Iritis	
Renal (reported as AESI if Grade $\geq 2$ )		
Nephritis	Nephritis autoimmune	Renal Failure
Renal failure acute	Creatinine elevations (report as AESI if Grade $\geq 3$ or any grade resulting in dose modification or use of systemic steroids to treat the AE)	
Skin (reported as AESI for any grade)		
Dermatitis exfoliative	Erythema multiforme	Stevens-Johnson syndrome
Toxic epidermal necrolysis		
Skin (reported as AESI if Grade $\geq 3$ )		
Pruritus	Rash	Rash generalized
Rash maculo-papular		
Any rash considered clinically significant in the physician's judgment		
Other (reported as AESI for any grade)		
Myocarditis	Pancreatitis	Pericarditis
Any other Grade 3 event which is considered immune-related by the physician		

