**CONFIDENTIAL**

Objectives	Endpoints
To evaluate the clinical measures of efficacy of belantamab mafodotin and aOX40 in participants with RRMM	
 
Clinical activity measured as Overall Response Rate (ORR) according to the International Myeloma Working Group (IMWG) Response Criteria (Kumar, et al., 2016)
 

Secondary	
To further evaluate the clinical measures of efficacy of belantamab mafodotin and aOX40 in participants with RRMM	Rates of: 
 
Partial Response (PR);
 
Very Good Partial Response (VGPR);
 
Complete Response (CR);
 
Stringent Complete Response (sCR)
 

To describe the exposure of belantamab mafodotin when administered in combination with aOX40 in participants with RRMM	
 
Belantamab mafodotin observed concentration
 

To describe the exposure of aOX40 when administered in combination with belantamab mafodotin.	
 
Combination of belantamab mafodotin with aOX40 treatment's observed concentration.
 

To assess anti-drug antibodies (ADAs) against belantamab mafodotin and against combination treatments (biologics) that are administered by IV infusion.	
 
Incidence and titers of ADAs against belantamab mafodotin and its combination with aOX40, when measured.
 

To further determine the safety and tolerability of belantamab mafodotin in combination with aOX40	
 
AEs of special interest for belantamab mafodotin
 
AEs of special interest for belantamab mafodotin in combination with aOX40
 
Ocular findings on ophthalmic exam
 

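### The catch-all row of protocol Table 11 conflicts with its heading and, read literally, leaves unlisted Grade 4–5 immune-related events outside the AESI definition

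*Protocol*

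**What the plan says.** Protocol Section 8.3.10 introduces Table 11 (Immune-related AEs for GSK'998 Treatment) with the rule that "Any event that meets the criteria described below must be reported", whatever cause the investigator assigns. Sites must enter these events in the eCRF and supply further information on each. The same paragraph adds: "Please note this table lists known AESI, additional events may be identified during the course of the study".

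The final block of Table 11 is headed "Other (reported as AESI for any grade"). It lists myocarditis, pancreatitis and pericarditis, and ends with the row "Any other Grade 3 event which is considered immune-related by the physician".

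SAP Table 2 names "AEs of special interest for belantamab mafodotin in combination with aOX40" as a secondary endpoint. SAP 4.5.2.1 gives no GSK'998 list of its own and refers to protocol Section 8.3.10. SAP 4.5.2.1.1 plans a summary of all immune-related AEs (irAEs) by system organ class, preferred term and maximum grade, with a listing.

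**The concern.** The catch-all row is where a toxicity that nobody anticipated would be classified. The protocol calls this the first study of the combination (Section 2.3.3) and says that data on the immune-related effects of GSK'998 are still insufficient (Table 6). A catch-all that names one grade takes in an unlisted Grade 3 event and, on its wording, omits a worse one. The block heading points the other way, so a site or a programmer cannot tell from the table which rule applies.

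Two things depend on the answer: whether the AESI reporting duty and supplemental information apply to such an event, and whether it carries the AESI flag behind a listed secondary endpoint.

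**Working it through.** The plan states no figure on this point, so the check is a comparison of texts.

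**1. How the table writes severity limits.** The pneumonitis, colitis, endocrine, haematologic, hepatic, ocular, renal and second skin headings use Grade ≥2 or Grade ≥3, as do the creatinine and hyperglycaemia rows. The signs survive in all of these, so a sign lost from this one row in text extraction is unlikely. One other row uses a bare grade: "Any Grade 4 anemia regardless of underlying mechanism". It stands in a block headed Grade ≥3.

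**2. Whether a row or its heading governs.** Creatinine elevations carry their own Grade ≥3 limit inside a renal block headed Grade ≥2. Hyperglycaemia carries its own condition inside the endocrine block. In both, the row narrows the heading. On that pattern, the Grade 3 limit in the last row governs. If the heading governed instead, the grade in the row would do no work.

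**3. Coverage of unlisted immune-related events under each reading.**

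| Reading | Grade 1–2 | Grade 3 | Grade 4–5 |
|---|---|---|---|
| Row governs, as worded | no | yes | no |
| Heading governs | yes | yes | yes |
| Row amended to Grade ≥3 | no | yes | yes |

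**4. Whether the text before the table settles it.** It allows further events to be identified but gives no grade rule for them, and it ties mandatory reporting to the criteria in the table.

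**5. Where an unlisted Grade 4–5 event would still be reported.**
- SAP 4.5.2: summaries of all AEs and of SAEs by maximum grade, and listings of all AEs and of fatal and non-fatal SAEs.
- SAP 4.5.2.1.1: the irAE summary and listing, with no lower or upper grade limit.
- Protocol Tables 3 and 5, footnotes: immune-related AEs and SAEs are collected to 90 days after the last dose, with no grade limit.

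The SAP does not say how irAEs are identified. If the flag comes from Table 11, whose title is immune-related AEs, the same gap enters that summary. If it is the investigator's judgement, it does not.

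**6. Who is affected.** SAP Section 5 gives 6 participants at dose level 1 and 3 at dose level 2: 6 + 3 = 9. SAP Section 2 states that no hypothesis is tested.

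**The case against.** The strongest reply is that exclusion is only one reading. If the any-grade heading governs, Grades 4 and 5 are covered. A row on clinically significant rash, in a block headed Grade ≥3, shows that row wording need not always narrow its heading, and the anaemia row shows that bare grades occur elsewhere. This stands in part: the exclusion is a literal reading and not a certainty. But the other reading makes every unlisted Grade 1–2 immune-related event an AESI and leaves the Grade 3 limit without meaning. Neither reading is clean.

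The second reply is that other rules catch the worst events. Protocol Section 6.6.2 requires contact with the Medical Director for clinically significant, non-haematological, drug-related toxicities of Grade ≥3 that may warrant interrupting or stopping treatment. Section 8.3.5 concerns potentially life-threatening AEs, but its content is in the Master Protocol, which was not available. Sites are also urged to notify promptly any event that might be an AESI. These provisions make it unlikely that the sponsor would not hear of such an event. As far as the supplied text shows, they do not make it an AESI or trigger the supplemental information.

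The third reply is that the SAP is based on Amendment 5 (21-JAN-2022), while the protocol supplied is Amendment 4. The section to which the SAP points may already be corrected. This cannot be checked here and belongs in the fix.

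A reader might go further and infer that severe immune-related toxicity would go unreported, or calculate how far one missed event would move an AESI percentage among nine participants. The documents support neither. The general AE, SAE and irAE outputs hold these events. For AESIs other than ocular ones, the SAP specifies the irAE summary and listing and defines no AESI rate from Table 11 that could be moved.

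**Conclusion.** The point holds in a limited form, at minor severity. The last row of Table 11 and its heading contradict each other, and nothing in the supplied text resolves the contradiction. Read literally, the row leaves unlisted Grade 4–5 immune-related events outside the AESI definition, and so outside its mandatory reporting and supplemental-information requirement.

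The possible loss is AESI classification and AESI-specific data, not capture of the events. It concerns at most nine participants in a descriptive analysis, in a sub-study already closed to enrolment. There is no evidence that any such event occurred or was missed, and sites may well have reported one as an AESI anyway.

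This rests on two assumptions: that the Amendment 4 wording of Section 8.3.10 still applies, and that the Master Protocol, Master SAP, study manual and eCRF guidance, none of which was available, give no overriding grade rule. If irAEs are flagged from Table 11 and not by the investigator, the gap also reaches the irAE summary.

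**What to change.** 1. Check whether Amendment 5 already rewords the row. If not, reconcile row and heading so that the catch-all does not exclude grades above 3. One way is to write the row as Grade ≥3 and give it a header of its own with the same limit, separate from the any-grade block.
2. In SAP 4.5.2.1 and 4.5.2.1.1, state how GSK'998 AESIs and irAEs are identified (investigator flag, term list or both), the grade rule used for each flag, and that it applies to all data already collected.
3. Look back once over Grade 4–5 events in the nine participants and apply the rule to any that the investigator judged immune-related.

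The cost is a few words in Table 11, one or two sentences in the SAP and a short listing review. No analysis has to be redesigned.

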#### 8.4. Treatment of Overdose

Guidelines for management of belantamab mafodotin overdose are contained in the 208887 MP Section 8.4.

There is no specific antidote for overdose with GSK3174998 (aOX40). In the event of a suspected overdose, it is recommended that the appropriate supportive clinical care should be instituted, as dictated by the subject's clinical status.

- 8.5. Pharmacokinetics**
- 8.6. Genetics**
- 8.7. Immunogenicity Assessments**
- 8.8. Biomarkers**
- 8.9. Health-Related Quality of Life**

## **9. STATISTICAL CONSIDERATIONS**

Please refer to the 208887 MP for the overall Statistical Considerations for the study.

- 9.1. Statistical Hypotheses**
- 9.2. Sample Size Determination**
- 9.3. Populations for Analyses**
- 9.4. Statistical Analyses**
- 9.5. Interim Analysis**
- 9.6. Sample Size Sensitivity**

## **11. GUIDELINES FOR DOSE MODIFICATION AND OTHER PARTNER COMBINATION TREATMENTS FOR ALL SUBSTUDIES**

Please refer to the 208887 MP for the overall Guidelines for Dose Modification for the study.

## **12. SUPPORTING DOCUMENTATION AND OPERATIONAL CONSIDERATIONS**

Please refer to the 208887 MP for the overall Supporting documentation and operational considerations for the study.

Any information and details specific to Sub-study 1 are in Section 12.12 and Section 12.13 below.

- 12.1. Appendix 1: Regulatory, Ethical, and Study Oversight Considerations**
- 12.2. Appendix 2: Clinical Laboratory Tests**
- 12.3. Appendix 3: AEs: Definitions and Procedures for Recording, Evaluating, Follow-up, and Reporting**
- 12.4. Appendix 4: ECOG Performance Status**
- 12.5. Appendix 5: NYHA Functional Classification System**
- 12.6. Appendix 6: Modified Diet in Renal Disease**
- 12.7. Appendix 7: Contraceptive Guidance and Collection of Pregnancy Information**
- 12.8. Appendix 8: Genetics**
- 12.9. Appendix 9: Liver Safety: Required Actions and Follow-up Assessments and Study Treatment Rechallenge Guidelines**
- 12.10. Appendix 10: Eye Care Specialist- Qualifications and Requirements**
- 12.11. Appendix 11: Home Healthcare and Telemedicine Approaches**

**12.12. Appendix 12: Abbreviations and Trademarks**

ADA	Anti-drug antibody
ADC	Antibody drug conjugate
ADCC	Antibody dependent cellular cytotoxicity
AE	Adverse event
AESI	Adverse events of Special Interest
ALT	Alanine aminotransferase
AST	Aspartate aminotransferase
AUC	Area under the concentration-time curve
BCMA	B cell maturation antigen
BCVA	Best corrected visual acuity
CBC	Complete blood count
CBR	Clinical benefit rate
CE	Cohort Expansion phase
cfDNA	Cell-free deoxyribonucleic acid
CI	Confidence interval
CK	Creatine kinase
CL	Clearance
C max	Maximum plasma drug concentration
CMMC	Circulating multiple myeloma cells
CPMS	Clinical Pharmacology Modeling and Simulation
CR	Complete response
CRP	C-reactive protein
CRT	Calreticulin
CT	Computer tomography
CTCAE	Common Toxicity Criteria for Adverse Events
Cys-mcMMAF	cys Monomethyl auristatin F
DAMP	Damage-Associated Molecular Pattern
DC	Dendritic cells
DE	Dose Exploration phase
DIC	Disseminated intravascular coagulation
DoR	Duration of response
DLBCL	Diffuse large B-cell lymphoma
DLT	Dose limiting toxicity
DNA	Deoxyribonucleic acid
EC	Ethics committee
ECG	Electrocardiogram
ECHO	Echocardiogram
ECOG	Eastern Cooperative Oncology Group
eCRF	Electronic case report form
eGFR	Estimated Glomerular Filtration (eGFR)
EOI	End of infusion

EORTC QLQ	European Organisation for Research and Treatment of Cancer Quality of Life Questionnaires
FISH	Fluorescence in situ hybridization;
FLC	Free light chain
FSH	Follicle stimulating hormone
FTIH	First time in human
GFR	Glomerular filtration rate
GSK	GlaxoSmithKline
GSK2857914	GlaxoSmithKline anti-BCMA antibody (CA8 J6M0 Potelligent)
GSK2857916	GlaxoSmithKline anti-BCMA antibody drug conjugate (CA8 J6M0 Potelligent MMAF)
HBs-Ag	Hepatitis B surface antigen
HBc	Hepatitis B core
HbcAb	Hepatitis B core antibody
HBV	Hepatitis B
HCV	Hepatitis C
HMGB1	High mobility group box 1
ICD	Immunogenic cell death
ICF	Informed consent form
ICH	International Council on Harmonization
IEC	Institutional ethics committee
Ig	Immunoglobulin
IHC	Immunohistochemistry
IMWG	International Myeloma Working Group
IP	Investigational Product
IRB	Institutional review board
IRR	Infusion-related reaction
ITT	Intent-to-treat
IV	Intravenous
LBCL	Large B-cell lymphoma
LFT	Liver function test
LLN	Lower limit of normal
LVEF	Left ventricular ejection fraction
mAb	Monoclonal antibody
MDRD	Modified diet in renal disease
MedDRA	Medical Dictionary for Regulatory Activities
MM	Multiple Myeloma
MMAF	Monomethyl auristatin F
MoA	Mechanism of action
MP	Master Protocol
MR	Minimal response
MRD	Minimal residual disease
MRI	Magnetic resonance Imaging
MTD	Maximum Tolerated Dose
NCI-CTCAE	National Cancer Institute – Common Toxicity Criteria for Adverse Events

NT-proBNP	N-terminal B-type natriuretic peptide
NK	Natural killer
NYHA	New York Heart Association
ORR	Overall response rate
OS	Overall survival
OSDI	Ocular Surface Disease Index
PBMC	Peripheral blood mononuclear cells
PD	Progressive disease
PET	Probability of early termination
PFS	Progression-free survival
PI	Proteasome inhibitor
PK	Pharmacokinetic(s)
PR	Partial response
PRO	Patient reported outcome
Q3W	Every 3 week
QoL	Quality of life
RAP	Reporting and analysis plan
RNA	Ribonucleic acid
RO	Receptor occupancy
RP2D	Recommended Phase 2 dose
RRMM	Relapsed/refractory multiple myeloma
SAE	Serious adverse event
sBCMA	Soluble B-cell maturation antigen
sCR	Stringent complete response
SD	Stable disease
SoA	Schedule of Activities
SoC	Standard of care
SOI	Start of infusion
SPEP	Serum protein electrophoresis
SRM	Study research manual
t 1/2	Half-life
TTP	Time to progression
TTR	Time to response
ULN	Upper limit of normal
UPEP	Urine protein electrophoresis
VGPR	Very good partial response
WOCBP	Women of childbearing potential

### Trademark Information

Trademarks of the GlaxoSmithKline group of companies
None

Trademarks not owned by the GlaxoSmithKline group of companies
None

## 12.13. Appendix 13: Protocol Amendment History

The Protocol Amendment Summary of Changes Table for the current Amendment 04 is located directly before the Table of Contents (ToC).

### Protocol Amendment 3 (08-JUL-2020)

#### Germany Participation

Sub-study 1 is not applicable for Germany at this time and centers in Germany will not participate in Sub-study 1.

### Protocol Amendment 3 Summary of Changes Specific to Sub-study 1

The protocol has been amended to introduce a new sub-study into Section 14 of the protocol. In addition, changes were made in line with comments from regulators, program level changes and safety updates, which include the following:

- Removal of post-baseline ECG assessments
- Modifications to the Dose Escalation Plan (DEP)
- Revised guidance added for belantamab mafodotin overdose
- Revisions to statistical projections and analyses due to addition of Sub-study 4
- Replaced asset number or abbreviations with generic name belantamab mafodotin
- Included reference Lonial, 2020 to support 2.5 mg/kg starting dose and removal of references to 3.4 mg/kg dose
- Guidance on dose modifications modified to include/change management of IRRs, urine dipstick results, thrombocytopenia, neutropenia without fever, pneumonitis
- Modified text on Risk Assessment for thrombocytopenia, potential cardiotoxicity, immunosuppression
- Minor editorial and document formatting revisions

Section # and Name	Description of Change	Brief Rationale
Revised Study Design		
Section 11.6	Change from 4 to 3 dose levels	See Lonial, 2020 reference for monotherapy recommended dose
Section 11.12.1	Added exclusion for recent symptomatic pericarditis	To better define appropriate study population
Safety Changes		
Section 11.8.2	Change dose reduction table	As above, see Lonial, 2020 reference for monotherapy recommended dose.
Section 11.8.4	Added section on aOX40 overdose	To provide available guidance on overdose
Changes in Assessments and SoAs		
Section 11.2	Specified follow-up ADA assessment for aOX40	Clarified immunogenicity assessments

Section # and Name	Description of Change	Brief Rationale
Section 11.2	Revised assessments and descriptions, including: Urinalysis assessment and description Removal of post-baseline ECG assessments, NT-proBNP, troponin Description of MRI, CT, PET/CT scans for disease assessment in Germany	Provide clarifications and more specific guidance, as with Master Protocol
Section 11.2	Added optional follow-up Qualitative phone interview	Clarified timepoint assessment for qualitative phone interview
Protocol Clarification and Alignment		
Section 11.2	Replace ophthalmologist and optometrist with eye-care specialist term and define same	Simplify and define provider terminology
Section 11.2,	Revisions to QoL assessments to include IL52 (symptom assessment) portion of EORTC QLQ-My20 and revise timepoints	Clarify assessments and timing Updated QoL assessment reflects disease symptom portion of
Throughout	Asset numbers/abbreviations replaced with generic names except for laboratory sampling	For consistency throughout document
Editing, format, style changes		
Throughout	Correction of typos and technical document aspects	Minor changes with no impact on content

